10.2 Handling and Reporting of Infusional and Temporally Related Adverse Events

10.2.1 Common Temporally Associated AEs or ADRs

Common temporally associated AEs or ADRs that may occur in approximately 5% of infusions or less include but are not limited to headache, fatigue, chills, dyspnea, pallor, backache, other body ache, leg cramps, light-headedness, fever, urticaria, flushing, elevation of blood pressure, nausea, vomiting, anaphylactic reactions, infusion site reactions, hypersensitivity reactions, oliguria, and anuria.

On rare occasions, immunoglobulins may cause a sudden fall in blood pressure and, in isolated cases, anaphylactic shock, even when the subject has shown no hypersensitivity to previous administrations. Cases of reversible aseptic meningitis, isolated cases of reversible hemolytic anemia/hemolysis and rare cases of transient cutaneous reactions, have been observed with human normal immunoglobulin. Transfusion-related lung injury (TRALI) characterized by severe respiratory distress, pulmonary edema, fever, hypoxemia, and abnormal left ventricular function have also been reported, typically within 1 to 6 hours after the transfusion. Increases in serum creatinine levels and/or acute renal failure have been observed. Very rarely, thromboembolic reactions such as myocardial infarction, stroke, pulmonary embolism, and deep vein thrombosis may occur.

10.2.2 Subject Monitoring

The recommended infusion rates mandated by the protocol must be closely followed. Subjects must be closely monitored and carefully observed for any symptoms throughout the infusion period as per the protocol requirements.

Certain severe ADRs may be related to the rate of infusion.

Certain adverse reactions may occur more frequently:

- in patients with hypo- or agammaglobulinemia with or without IgA deficiency
- in case of high rate of infusion

All subjects will be monitored for the first hour after each infusion, except for the first infusion where they will be monitored for 3-4 hours after the infusion. During this time, the subject will be observed in order to detect potential adverse signs and conduct the post-infusion 60-minute vital sign measurement and assessment for signs of hemolysis or thrombosis. Handling of Infusional and Temporally Associated AEs

Infusional and temporally associated AEs will be closely monitored. For AEs that occur during infusions, the infusion rate in effect at the time of onset of the AE will be captured.

IMP will be administered according to the infusion rate titration schedule in Section 13.6.

Note: The dose and administration of CP for subjects on the Waiting Period will be per standard care, as determined by the Investigator in consultation with the treating physician.

If an infusional AE occurs during the first treatment course, the study staff will initiate one of the following actions, which will be graded from 1 to 4 depending on the nature and/or severity of the event:

1. Reduce the current infusion rate to one-half the rate of the infusion at which the AE was observed; or
2. Reduce the rate of the infusion more than one-half the rate at which the AE was observed, as necessary to subside symptoms; or
3. Reduce the rate of the infusion to one-half, or progressively reduces more than one-half, the rate at which the AE was observed and then stops the infusion, as necessary to subside symptoms; or
4. Stop the infusion to subside symptoms.

The study staff will evaluate the subject's AE and then:

- increase or resume the infusion at a rate tolerated by the subject once the symptoms have subsided; or

- stop the infusion and not resume it.

If a subject has an infusional AE at the same infusion rate twice, then subsequent infusion rate escalation, if any, should be halted at the rate before the AE, depending on the severity of the AE.

10.2.3 Reporting Infusional and Temporally Associated AEs

Infusional and temporally associated AEs will be reported as the number occurring during the infusion and within 1 hour, 24 hours, and 72 hours after the end of the infusion, and the total number of AEs that occur during or within 72 hours of an infusion will be given in the *Adverse Reactions* section of the product's draft package insert, along with the total number of infusions, and the mean number of such temporally associated AEs per infusion (see Section 12.3.4).

10.3 Eliciting and Reporting of Other Adverse Events

AEs will be captured from signing of Informed Consent/Assent to until 21±4 days or 28±4 days following the last infusion. AEs and ADRs will be elicited and reported as follows:

The condition of the subject will be monitored throughout the study. At each visit, AEs will be elicited using a standard non-leading question such as "*How have you been since the last visit / during the previous study period?*" AEs will also be elicited through the use of Subject Diary cards, which the Investigator will review in detail with the subject at each visit, ensuring accuracy and completeness of entries recorded by the subject.

The staff will also ask specific questions during phone calls to determine whether a work-up for hemolysis and/or thrombosis is necessary. During the phone calls, the staff will ask open-ended questions about the subject's wellbeing and to ensure that AEs are being documented in the Subject Diary. The study staff will review these specific questions with the subject and ensure subject is completing the diary. (Section 6.12.3)

Any AE or ADR occurring during the study will be noted in detail on the appropriate pages of the eCRF. If the subject reports several signs or symptoms, which represent a single syndrome or diagnosis, the latter should be recorded in the eCRF. The Investigator will grade the severity of all AEs or ADRs (mild, moderate, or severe), the seriousness (non-serious or serious) and relatedness, with final determination of causality established by the Sponsor, as defined in Section 10.1.

In the event of abnormal laboratory findings considered clinically significant by the Investigator, the tests will be repeated and followed-up, as needed. Diseases, signs and symptoms, and/or laboratory abnormalities already existing before the first administration of IMP are not considered as AEs when observed at a later stage unless they represent a worsening.

The Investigator should always provide detailed information concerning any abnormalities and the nature of, and reasons for any necessary action(s), as well as any other observations or comments, which are useful for the interpretation and understanding of the subjects' AEs or ADRs.

10.4 SAE Reporting

All AEs assessed as serious must be reported beginning from the signing of Informed Consent/Assent to 21±4 days or 28±4 days following the last infusion. SAEs must be followed until the event resolves, the event or sequelae stabilize, or it is unlikely that additional information can be obtained after demonstration of due diligence with follow-up efforts (i.e., the subject or Investigator is unable to provide additional information or, the subject is lost to follow-up).

10.4.1 SAE Reporting to Safety

All SAEs will be reported within 24 hours of the Investigator becoming aware of the event and submit the Safety Report 24/7 to the Safety Department via the fax number/email below.

Toll Free [contact]. Toll Free [contact]

Email: [contact]

Full details of SAE reporting to the Safety Department will be defined in the Safety Management Plan.

It should be noted that reporting to the Safety Department within 24 hours of awareness is required for all SAEs regardless of their causal relationship with the IMP.

The Safety Department, together with the sponsor's medical monitor, will review all safety information/documentation and follow up with the investigative site to obtain any other required information. Follow-up information should be actively sought by the Investigator and reported to the Safety Department as it becomes available using the Safety Report.

The sponsor and the appointed for the study are responsible for reporting SAEs to the FDA/appropriate regulatory authority for trials outside the US, as applicable.

Serious adverse events that are unusual in the absence of drug therapy will be listed in the *Adverse Reactions* section of the draft package insert, even if there are only one or two reported events, unless it is clear that a causal relationship can be excluded.

10.4.2 Institutional Review Board/Independent Ethics Committee

A central IRB will be used for the majority of the sites in the US, and local IRBs/IECs for the remaining US sites and for the Russian sites. All AEs will be reported to the IRB/IEC according to the guidelines of the IRB/IEC. However, as a general guideline, IRBs need

to know about any AEs that are unknown or of a greater severity than what is reported in the Investigator's Brochure. Reporting is always required for all SAEs. Any new safety data (or other finding) that might alter the assessment of an IRB/IEC regarding their risks versus benefits analysis should always be reported to the IRB/IEC. The sponsor and the clinical research associate (CRA) will assist the Investigator in determining which events require reporting and in what timeframes.

10.4.3 Expedited Suspected Unexpected Serious Adverse Reaction (SUSAR) Reporting (Sponsor Responsibility)

The Sponsor will submit a written IND Safety Report (i.e., completed FDA Form 3500A) within 15 calendar days of receipt to the responsible new drug review division of the FDA for any observed or volunteered AE that is determined to be:

1. associated with the investigational drug or study treatment(s);
2. serious; and
3. unexpected.

In addition, if the event is fatal or life-threatening and meets the above criteria, a telephone or facsimile notification will be sent to the FDA as soon as possible, but no later than 7 calendar days after the sponsor's initial receipt, followed by a completed FDA Form 3500A within 15 calendar days after initial receipt.

Each IND Safety Report will be prominently labeled "IND Safety Report," and a copy will be provided to all participating site Investigators.

For each written IND Safety Report, the Sponsor will identify all previously submitted IND Safety Reports that addressed a similar adverse event experience and will provide an analysis of the significance of the newly reported adverse event in light of the previous, similar report(s).

If the results of the Sponsor's follow-up investigation show that an adverse event that was initially determined to not require a written IND Safety Report does, in fact, meet the requirements for reporting, the Sponsor will submit a written IND Safety Report as soon as possible, but in no event later than 15 calendar days after the determination was made.

Follow-up information to an IND Safety Report will be submitted to the applicable review division of the FDA as soon as the relevant information is available.

For study sites outside of the United States, the corresponding reporting procedures will be followed according to local regulations.

10.5 Pregnancy

Every effort will be made to avoid a pregnancy during the study. Contraceptives against pregnancy should be used (see Section 4.3.1), and the contraceptive techniques discussed

between the PI and subject at Screening should not be changed during the course of the study. A pregnancy test will be performed at all visits.

In case a subject becomes pregnant during the study, she has to be withdrawn from the study. Pregnancies occurring during the study after exposure to the IMP must be reported. The pregnancy notification form has to be sent to the Safety Department. Follow-up information on the outcome of both mother and fetus must also be reported.

10.6 Procedure for Breaking the Blind

As this is an open-label study, no subject or study personnel will be blinded.

10.7 Follow-up of Adverse Events

The responsible Investigator will follow up each AE through the LTSV or LTSF (as applicable) until it is resolved or until the medical condition of the subject is stable. AEs that are not resolved or stable at the time of study completion will be recorded as ongoing. All relevant follow-up information will be reported to the sponsor.

11 Pharmacokinetic Analysis

For all subjects in the PK sub-study, blood samples will be collected for the assessment of serum concentrations of total IgG. The serum concentrations will be determined as defined in a laboratory assay plan. All PK parameters will be estimated by both compartmental and non-compartmental analysis using Phoenix® WinNonlin 6.3 (Pharsight) and summary statistics will be presented. For all subjects in the all treated population dataset, prior to each infusion, trough serum IgG concentrations will also be determined. The data will be baseline (predose) corrected for the PK analysis.

The area under the concentration-time curve over 1 dosing interval (AUC_{0-t}), the area under the concentration-time curve extrapolated to zero concentration (AUC_{0-inf}) the maximum serum concentration (C_{max}), the time to reach the maximum serum concentration (T_{max}), the volume of distribution at steady-state (V_{ss}), mean residence time (MRT), the total body clearance (Cl), and the terminal half-life ($t_{1/2}$) will be determined from the total IgG serum concentrations measured at infusion of IMP at Infusion 6 (week 15 ± 2 days) for 21-day cycle subjects or Infusion 5 (week 16 ± 2 days) for 28-day cycle subjects (using the trough level immediately prior to this infusion as baseline). An additional sample will also be taken prior to the next infusion at Week 18 (± 2 days), Infusion 7 for subjects on a 21-day cycle, or at Week 20 (± 2 days), and Infusion 6 for subjects on a 28-day cycle.

12 Statistical Analysis

12.1 Analysis Populations

The safety analysis set will consist of all subjects who are enrolled into the study and received study product. The all treated population analysis set will be the same as the safety set. A modified per-protocol population analysis set will be defined as all subjects in the full all treated population set who remain in the study for at least 6 infusions.

A per-protocol (PP) analysis set will consist of all subjects in the all treated population set who complete the whole 12-month study period and who do not have any major protocol violations as described in the Data Handling Plan.

The analyses described below will be presented for all subjects in the all treated population, the modified PP population, and the PP population as follows:

- Cohort 1 only;
- Cohort 2 only;
- Each of the 3 age groups within Cohort 2;
- Cohorts 1 and 2 pooled.

The primary efficacy analysis will be based on the all treated population analysis set, with separate analyses for Cohort 1 and Cohort 2.

12.2 Handling of Missing Data

For the primary efficacy analysis, the method of maximum likelihood estimation will be used in conjunction with a negative binomial model to obtain a 99% one-sided upper confidence limit on the rate of serious bacterial infections. Since the resulting confidence interval leads to valid statistical inference assuming missing data are missing at random, no data imputation will be used in this analysis. With respect to safety and secondary endpoints, no data imputation will be used in the analysis of any other data from this study including the PK evaluations. Missing data will be omitted from summary statistics.

12.3 Statistical Analysis Plan

12.3.1 Descriptive analyses

Continuous variables will be summarized using a standard set of descriptive statistics, consisting of frequency count, mean, standard deviation, median, maximum, and minimum. Time to event endpoints will be presented using Kaplan-Meier plots. Binary endpoints and categorical data will be summarized by count and percentage. Count data will be summarized by total counts and rates per subject per infusion.

12.3.2 Primary Efficacy Endpoint

The primary efficacy endpoint in this clinical study is the rate of acute serious bacterial infections (pneumonia, bacteremia and septicemia, osteomyelitis/septic arthritis, bacterial meningitis, visceral abscess) per subject during the 12-month study observation period while receiving IMP. Serious bacterial infections (SBIs) must be confirmed with the tests and outcomes as described in Section 21.1.

The rate of occurrence of such infections will be calculated for each subject as $52n/w$ where n is the number of reported infections and w is the number of weeks on study.

For the primary endpoint, a 99% one-sided (upper) confidence limit for the incidence rate of SBIs (scaled to represent 12 months exposure if necessary) will be derived, and the objective of demonstrating that the true infection rate is below 1 per subject per year will be considered established if this upper limit is less than 1.

To calculate the confidence limit, a negative binomial regression model will be used. This model includes an over-dispersion parameter to account for possible intra-subject correlation as well as the actual time period each subject is on the study as an offset variable. The null hypothesis for this analysis is that the true SBI rate is at least 1 per subject per year, and the alternative hypothesis is that this rate is less than 1 per subject per year. Rejection of the null hypothesis is therefore equivalent to demonstration of the study objective to show that the true rate is less than 1 per subject per year.

The proposed method of analysis makes appropriate allowance for any intra-subject correlation in the incidence of SBIs. Such correlation would occur whenever variability in the individual subject-specific SBI rates exceeds what would be expected in the presence of true Poisson variability. The proposed statistical test based on a negative binomial model includes an overdispersion parameter reflecting any such inflated variance.

No formal statistical analyses will be done comparing the primary efficacy endpoint between the Waiting Period and the IMP Treatment Period.

12.3.3 Secondary Efficacy Endpoints

Secondary endpoints are:

- Total serum IgG trough levels
- Number of episodes of fever ($\geq 100.4^{\circ}\text{F}$)
- Number of days out of work/school/kindergarten/day care or unable to perform normal daily activities due to infection
- Number of days of hospitalization due to infection
- Number of days of antibiotic use for infection prophylaxis and/or treatment

- Number and duration of infections other than acute serious bacterial infections

These endpoints will be analyzed descriptively, using frequency tables or the standard set of summary statistics as appropriate.

No formal statistical analyses will be done comparing secondary efficacy endpoints between the Waiting Period and the IMP Treatment Period. However, any efficacy endpoints measured during both the Waiting Period on commercial product and IMP Treatment Period may be summarized side-by-side using the appropriate descriptive statistics. For the Waiting Period, the summary descriptive statistics will be aggregated over all commercially licensed products.

12.3.4 Safety Endpoints

Evaluation of safety includes the analyses of laboratory investigations, adverse events, and adverse reactions/suspected adverse reactions. No formal statistical analyses will be done comparing any of the safety endpoints between the Waiting Period on commercial product and the IMP treatment period. However, all safety endpoints measured during both the Waiting Period on commercial product and the IMP treatment period will be summarized side-by-side using the appropriate descriptive statistics. For the Waiting Period on commercial product, the summary descriptive statistics will be aggregated over all commercially licensed products.

Laboratory Data:

A summary by treatment period (Waiting period, IMP treatment period) will be produced for each of the laboratory parameters at each visit. These safety summaries will include descriptive summary tables and the data will be summarized in the form of frequency count, mean, standard deviation, median, minimum and maximum by treatment period and visit.

Adverse Events:

The seriousness, severity and relationship to the study drug of adverse events (AEs) will be observed and recorded on repeated administrations of the study drug using the MedDRA dictionary for the coding of AEs and serious adverse events (SAEs).

The number and proportion of subjects who have one or more AEs will be tabulated by seriousness, severity, and relationship to treatment according to body system and treatment period. Temporally related AEs will be similarly summarized. Rates of AEs will be estimated on a per infusion per subject basis and tabulated by seriousness, severity, and relationship to treatment according to body system and treatment period.

The following observations will be summarized, using the standard set of summary statistics (see 12.3.1).

- The number of infusions administered

- The total number of AEs experienced (irrespective of causality)
- The total number of AEs temporally associated with infusions
- During the infusion
- Within 1 hour after the infusion
- Within 24 hours after the infusion
- Within 72 hours after the infusion
- The number and proportion of infusions with which one or more infusional AEs are associated
- The number of infusional AEs per infusion
- Rate-related AEs

AEs will also be tabulated for the 30 subjects who received the highest doses of IMP and commercial product.

The FDA recommends that for a novel IGIV formulation, a study should demonstrate that an upper 95% confidence limit on the rate of infusions having one or more temporally-associated AEs be less than 40 infusions per 100 patient infusions (0.40). An AE should be established as associated to the infusion of study drug by implicating temporal association (this includes all AEs regardless of relationship to product).

For the purpose of this study, AEs are considered temporally associated with the study drug infusion, if they occur in the period from the start of the infusion until 72 hours after the end of the infusion. To meet the recommended target for this safety endpoint, the number of infusions having one or more temporally-associated AEs will be analyzed using a negative binomial regression model with an over-dispersion parameter to account for possible intra-patient correlation and the number of infusions per patient as an offset variable. To calculate the required upper 95% confidence limit, an intercept-only negative binomial regression model will be fit to the data in which the response for each subject is the number of affected infusions (i.e., the number of infusions with one or more temporally-associated AEs). A two-sided 90% confidence limit on the intercept will then be computed on the inverse link scale to achieve an upper one-sided 95% confidence limit on the expected mean number of infusions per 100 patient infusions having one or more temporally associated AEs. This upper limit should be below 40 in order to demonstrate safety with respect to the infusion process.

Adverse Reaction/Suspected Adverse Reaction

The operational definition of adverse reaction/suspected adverse reaction for analysis purposes will be all AEs meeting any of the following criteria: (a) the event began during or within 72 hours following the last IMP infusion; (b) the event was considered by the

investigator and/or the sponsor to be at least possibly related to the IMP administration;
or (c) the causality assessment was missing or indeterminate.

β2GPI and to β2GPI-DI Antibody Data

Data on formation of antibodies to β2GPI and to β2GPI-DI will be tabulated and discussed individually in the text.

Viral Safety Data

Viral safety data will also be listed (not tabulated) and any seroconversions will be discussed individually in the text.

Hemolysis Data

Data on potential IGIV-associated hemolysis will be tabulated and discussed in the text. The operational definition of IGIV-associated hemolysis for this analysis is defined as any event meeting the following criteria occurring within 10 days following IGIV administration: (a) a fall of at least 1 g/dL in hemoglobin from the previous value; (b) a positive Coombs test (direct anti-globulin test); and (c) at least 2 of the following: increased reticulocyte count, increased LDH, low haptoglobin, increased bilirubin, increased plasma free hemoglobin, increased urine hemosiderin.

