6.8 General Safety Laboratory Assessments

Samples for general laboratory safety assessments will be collected at the following time points:

- **All subjects** at Screening
- **All subjects** before administration of IMP or CP at infusions 1 (baseline value), 2, 3 and 4 and then before every fourth infusion (8, 12, 16, etc.), TCTV (Treatment Completion/Termination Visit) and at the LTSV
- Post-Infusion **IMP treatment for Groups 1 and 2** during Safety Evaluation Phase
 - 7 days (± 1 day) after administration of IMP at infusions 1, 2, and 4 and then after every fourth IMP infusion (8, 12, 16) when IMP treatment ends;
- Post-Infusion **IMP treatment for Group 3**
 - 7 days (± 1 day) after administration of IMP at infusions 1 and 4

If it is difficult for subjects (particularly children) to return to the study site for these tests, blood samples may be drawn by a home healthcare nurse.

General safety laboratory assessments include the following tests:

Hematology

CBC, hemoglobin, hematocrit, white blood cell (WBC) count and differential, red blood cell (RBC) count, RBC indices (mean corpuscular volume [MCV], mean corpuscular hemoglobin [MCH], mean corpuscular hemoglobin concentration [MCHC], red cell distribution width [RDW]), and platelets

Blood chemistry

Glucose, total bilirubin, creatinine, lactate dehydrogenase (LDH), blood urea nitrogen (BUN), alanine aminotransferase (ALT), aspartate aminotransferase (AST)

Urinalysis

Protein, glucose, blood, bilirubin, urobilinogen, pH, and ketones by dipstick; sediment analysis

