6.9 Hemolysis

Tests for hemolysis include urine hemosiderin, serum haptoglobin, plasma free hemoglobin, Coombs test (direct anti-globulin test).

Samples for hemolysis assessments will be collected at the following time points:

- **All subjects** at Screening
- **All subjects** before administration of IMP or CP at infusions 1 (baseline value), 2, 3 and 4 and then every fourth infusion (8, 12, 16, etc.), TCTV and at the LTSV
- **Post-Infusion IMP treatment for Groups 1 and 2** during Safety Evaluation Phase
 - 2-3 days after administration of IMP after administration of IMP infusions 1 (baseline value), 2 and 4;
 - 7 days (± 1 day) after administration of IMP at infusions 1, 2, and 4 and then after every fourth infusion (8, 12, 16) until IMP treatment ends;
- **Post-Infusion IMP treatment for Group 3**
 - 7 days (± 1 day) after administration of IMP at infusions 1 and 4

If it is difficult for subjects (particularly children) to return to the study site for these tests, blood samples may be drawn by a home healthcare nurse.

For all subjects, a drop of ≥ 2.0 g/dL from the pre-infusion hemoglobin level or clinical signs of hemolysis between visits will lead to a full hemolysis work-up.

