11.5. Clinical Laboratory Evaluations

11.5.1. Hemolysis Data

The operational definition of IGIV-associated hemolysis for this analysis is defined as any event meeting the following criteria occurring within 10 days following IGIV administration:

- (a) A fall of at least 1 g/dL in hemoglobin from the previous value;
- (b) A positive Coombs test (direct anti-globulin test); and
- (c) At least 2 of the following: increased reticulocyte count, increased lactic dehydrogenase (LDH), low haptoglobin, increased bilirubin, increased plasma free hemoglobin, increased urine hemosiderin.

Data on potential IGIV-associated hemolysis will be summarized by cohorts and age groups for the CP and IMP Treatment Periods.

Additionally, as requested by FDA, a listing of hemolysis-related analytes across time for subject with >1 g/dL fall in hemoglobin from the mean of Screening and pre-IMP baseline values will be provided. Hemolysis analytes include urine hemosiderin, serum haptoglobin, plasma free hemoglobin, direct coombs test, LDH, and bilirubin.

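### Criterion (c) of the IGIV-associated hemolysis definition names a reticulocyte count that no scheduled panel measures, so Day 7 samples can be judged on only five of six markers and the rule may miss some events

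*Protocol*

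**What the plan says.** IGIV-associated hemolysis is a listed safety endpoint (Protocol 5.2). Its operational definition appears in the Protocol synopsis, Protocol 12.3.4 and SAP 11.5.1. It covers the 10 days after an infusion and has three parts, all required. Parts (a) and (b) are "a fall of at least 1 g/dL in hemoglobin from the previous value; (b) a positive Coombs test". Part (c) is "at least 2 of the following: increased reticulocyte count, increased LDH, low haptoglobin, increased bilirubin", and the list ends with raised plasma free hemoglobin and raised urine hemosiderin, making six markers.

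The scheduled tests are set out elsewhere:

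- **Protocol 6.8, hematology:** "CBC, hemoglobin, hematocrit, white blood cell (WBC) count and differential, red blood cell (RBC) count, RBC indices", then the individual red cell indices and platelets. The chemistry panel in the same section includes LDH and total bilirubin.
- **Protocol 6.9:** "Tests for hemolysis include urine hemosiderin, serum haptoglobin, plasma free hemoglobin, Coombs test".
- **SAP 11.5.1, listing of analytes over time:** "Hemolysis analytes include urine hemosiderin, serum haptoglobin, plasma free hemoglobin, direct coombs test, LDH, and bilirubin".

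Outside the schedule, a full hemolysis work-up follows a hemoglobin drop of 2.0 g/dL or more, or clinical signs between visits (Protocol 6.9, 8.1.3), or a positive examination one hour after infusion (6.12.2.1). After a positive telephone answer the investigator decides whether to do one (6.12.3.2). No section lists the tests in a work-up; 6.12 and 8.1.3 refer to the facility's standard of care.

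**The concern.** The definition uses a marker that the schedule does not collect. SAP 11.5.1 shows the mismatch within one section: it states the six-marker rule and then lists analytes covering only five of the six, plus the Coombs test.

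Two things are at stake. First, not measuring a marker can only leave the number of qualifying events unchanged or lower it. Second, subjects who happen to have a local work-up may be judged on six markers and the rest on five. Neither document says whether an unmeasured marker counts as not met or makes the event not assessable. Protocol 12.2 and SAP 6.3 rule out imputation (retest values aside), so the choice would fall to whoever programs the table.

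**Working it through.** The documents state no expected hemolysis count, so there is no planned figure to reproduce. The check has three steps.

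**1. Match the six markers to the scheduled panels.**

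| Marker in (c) | Scheduled in |
|---|---|
| LDH | Protocol 6.8, chemistry |
| Bilirubin | Protocol 6.8, chemistry |
| Haptoglobin | Protocol 6.9 |
| Plasma free hemoglobin | Protocol 6.9 |
| Urine hemosiderin | Protocol 6.9 |
| Reticulocyte count | nowhere |

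Five of six are scheduled. The footnotes to Tables 3 and 4 that name the tests do not add the sixth.

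**2. Match the samples to the 10-day window.** Protocol 8.1 puts general safety tests before infusion and on Day 7, and hemolysis tests before infusion, on Day 2 or 3, and on Day 7.

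| Sample | In window? | Hemoglobin for (a)? | Coombs for (b)? | Markers for (c) |
|---|---|---|---|---|
| Day 2–3 (Groups 1 and 2 only) | yes | not scheduled | yes | 3 |
| Day 7 ± 1 | yes | yes | yes | 5 |
| Next pre-infusion, 21 or 28 days ± 2 | no | yes | yes | 5 |

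Only Day 7 can establish a case from scheduled data alone, and there (c) works as two of five. Pooling Day 2–3 with Day 7 still gives only five distinct markers.

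**3. Size the possible loss.** An event is lost only if it meets (a) and (b), exactly one of the five measured markers is abnormal, reticulocytes are raised, and no work-up counted them.

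Assume that in a true case each marker is abnormal independently with the same probability p. Then:

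- P(at least 2 of n) = 1 − (1−p)ⁿ − np(1−p)ⁿ⁻¹
- Loss = P(at least 2 of 6) − P(at least 2 of 5) = p × 5p(1−p)⁴ = 5p²(1−p)⁴

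At p = 0.3:

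- Six markers: 1 − 0.1176 − 0.3025 = 0.580
- Five markers: 1 − 0.1681 − 0.3602 = 0.472
- Formula: 5 × 0.09 × 0.2401 = 0.108, which agrees

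| p | Six markers | Five markers | Loss (points) |
|---|---|---|---|
| 0.3 | 58.0% | 47.2% | 10.8 |
| 0.5 | 89.1% | 81.3% | 7.8 |
| 0.7 | 98.9% | 96.9% | 2.0 |
| 0.8 | 99.8% | 99.3% | 0.5 |
| 0.9 | 99.99% | 99.95% | 0.04 |

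Setting the derivative to zero gives 2(1−p) = 4p, so p = 1/3. The largest loss under this model is 5 × (1/9) × (16/81) = 80/729, or 11.0 points.

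**Does the work-up fill the gap?** Not fully. Its laboratory trigger is a fall of 2.0 g/dL, while the definition starts at 1 g/dL. A fall of at least 1 but less than 2 g/dL without clinical signs prompts no work-up. Where a work-up is done, nothing requires a reticulocyte count and nothing excludes one.

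**The case against.** The strongest reply is that the definition does not depend on reticulocytes: any two of the other five markers satisfy (c), and all five are drawn at Day 7. That is correct. A reader might infer that cases *are* under-counted, but the documents support only that some *may* be missed. The loss needs four conditions together, and its size rests on a p the documents do not give.

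A reader might also infer that every scheduled sample runs as two of five. It does not: Day 2–3 has three markers and no scheduled hemoglobin, and pre-infusion samples fall outside the window of the previous infusion.

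The plan already covers part of the problem. SAP 11.5.1 lists the Coombs test and the five measured markers over time for subjects with a hemoglobin fall above 1 g/dL, so many near-misses on IMP will be visible. SAP 11.5.3 summarizes work-up results. This helps, but the listing measures the fall from the mean of Screening and pre-IMP baseline, whereas the definition uses the previous value. A listing also does not state how (c) was judged.

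Finally, the consequence is limited. The hemolysis rules in Protocol 8.1.3 rest on clinical and laboratory diagnosis, not on this definition, and safety summaries are descriptive with no formal comparison between periods. Protocol 1.3 says fewer hemolytic events may be expected. A reader might link that to the omission, but it is not a tested hypothesis and nothing in the documents supports the link.

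**Conclusion.** The point holds as a mismatch between an endpoint definition and the schedule. A six-marker rule for a named safety endpoint can be judged on only five markers at the one scheduled sample that can establish a case. The direction of any effect is certain, because a missing marker cannot add events. The size is not: from about 11 points at p = 0.3 to under 0.1 at p = 0.9, on criterion (c) alone, assuming independent markers with a common p. The loss is therefore possible, not shown. It is most likely for hemoglobin falls of at least 1 but less than 2 g/dL without clinical signs.

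Few samples are available to begin with. Group 3, about 60 of 75 subjects, has Day 7 draws after IMP infusions 1 and 4 only, which is 2 of 17 or 2 of 13 infusions (12% or 15%). Adding a marker does not change that separate limit, but it is a reason to make each Day 7 sample fully evaluable.

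**What to change.** 1. Add reticulocyte count to the Protocol 6.8 hematology panel at the Day 7 post-infusion draws, where hematology blood is already taken, and to the analyte listing in SAP 11.5.1.
2. For samples already taken, state in SAP 11.5.1 that (c) was judged on the five measured markers. This may be the part with most practical effect, since Group 3 was cleared for dosing in December 2016 and SAP V2.0 is dated September 2018.
3. Tabulate the events that met (a) and (b) with exactly one marker positive. These are the only events a reticulocyte count could have completed, so the table bounds the real effect without any assumed p.

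The cost is one added assay at Day 7 draws, a sentence in the SAP and one table row. Items 2 and 3 need no new sampling.
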